# 15.2 DLTs, Deaths, Other Serious Adverse Events, and Other Significant Adverse Events

#### 15.2.1 Occurrence of DLTs

Analysis set: DLT

The occurrence of DLTs during the DLT evaluation period is a primary endpoint for both Parts A and B of the study. The DLT period for Part A is defined as the first 3 weeks of the study, following the start of the study intervention. The DLT period for Part B is defined as the first 4 weeks of the study, following the start of study intervention. The DLT Analysis Set will be used for the analysis of the primary endpoint. Please refer to Section 6.6.3 of the Clinical Trial Protocol MS201964-0001 for the detailed definition of a DLT. Determination of whether an AE is considered a DLT is made by the Investigator and specified on the "Adverse Events Details" eCRF page; this assessment is subsequently confirmed by the SMC.

A summary table of DLTs will include the following summaries:

- Number and percentage of subjects who experienced a DLT during the DLT evaluation period
- Number and percentage of subjects experiencing any AE during the DLT evaluation period.
- Number of DLTs experienced per subject: 1 /2 /≥3
- DLTs by SOC and PT

A listing of DLTs will include subject identifier, dose level, and all relevant variables from the "Adverse Events Details" eCRF page.

In addition, a DLT profile plot of all subjects in the Safety Analysis Set will be produced. This will show a closed square for all subjects who were considered evaluable (i.e. included in DLT Analysis Set) and did not have a DLT during the DLT period, an open square for those who experienced a DLT during the DLT period, and an open circle for those who were excluded from the DLT Analysis Set. This plot will have cohort number on the x-axis and dose level (mg) on the y-axis.

#### 15.2.2 Deaths

Analysis set: SAF

All deaths after first study intervention will be tabulated based on information from the "Death" eCRF page. The summary will be displayed by cohort dose level and will include:

- Number of deaths overall and by primary reason
- Number of deaths within 30 days after last dose of study intervention
- Number of deaths within 60 days after first dose of study intervention

In addition, date and cause of death will be provided in an individual participant data listing together with selected dosing information, presented separately for each intervention (date of first / last administration, dose, number of cycles/ fraction days, and relatedness to each study intervention). The listing will include columns for:

- AEs with fatal outcome
- Flag for death within 30 days of last study intervention
- Flag for death within 60 days of first study intervention
- Flag for death related to COVID-19

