4.1.1.3 Follow-Up Periods

Safety Follow-up

Part A, Part B, and Part FE

The Safety Follow-up period will be 30 days and 90 days after the last dose of avelumab for safety evaluation of the combination of study interventions.

Part B

In addition to the Safety Follow-up relating to the combination of study interventions after the last dose of avelumab, for Part B, the following RT Safety Follow-up periods are defined to assess potential toxicity of RT when administered in combination with M3814 and avelumab:

- Short-term RT Safety Follow-up: 30 days after the end of RT for evaluation of safety.
- Mid-term RT Safety Follow-up: 3 months after the end of RT to evaluate late signs of RT-induced toxicity on normal surrounding tissues.
- Long-term RT Safety Follow-up: 12 months after the end of RT, to evaluate RT-induced toxicities, by telephone call.

Long-Term Follow-up

Part A, Part B, and Part FE

Participants will be followed for survival and use of subsequent anticancer therapy until the end of the study. Participants without PD who are not receiving subsequent anticancer therapy after the End of Treatment Visit, will be followed every 8 weeks with radiographic disease evaluation for the first 6 months of the study and then every 12 weeks thereafter until PD according to Response Evaluation Criteria in Solid Tumors Version 1.1 (RECIST v 1.1), and for survival and use of subsequent anticancer therapy until the end of the study.

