Adverse events observed from the first dose until 30 days after last study intervention administration (i.e. TEAEs) will be summarized according to MedDRA system organ classes and preferred terms. The incidence and type of the following will be analyzed:

- TEAEs and SAEs
- TEAEs and SAEs related to study intervention
- TEAEs with NCI-CTCAE Grades ≥ 3
- TEAEs related to study intervention with NCI-CTCAE Grades ≥ 3
- AEs leading to withdrawal, dose modifications, or permanent study intervention discontinuation
- Deaths.

Participants who terminate treatment will be displayed in a by-participant listing and summarized by primary withdrawal reason.

All reported deaths after first dose of study intervention as well as reasons for death will be tabulated (for all participants enrolled). Deaths within 30 days from last dose administration and deaths beyond this period up to 90 days follow-up and reasons for them will also be tabulated.

Laboratory Variables

Laboratory results will be classified by grade according to NCI-CTCAE v 5.0. The worst on-study grades after the first study intervention will be summarized.

Shifts in toxicity grades from first treatment to highest grade will be displayed. Results for variables that are not part of NCI-CTCAE will be presented as below, within, or above normal limits. Only participants with postbaseline laboratory values will be included in these analyses.

Physical Examination

Physical examination, including vital signs (body temperature, respiratory rate, heart rate, and blood pressure), and 12-lead ECG, recorded at Baseline and after administration of study intervention will be presented.

Further details will be provided in the Integrated Analysis Plan.

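### The SAP omits the protocol's table of deaths more than 30 and up to 90 days after last dose, and does not declare the change

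*SAP*

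**What the plan says.** Protocol 9.4.2 (Safety Analyses) plans a table of all deaths after first dose with reasons. It then adds a split by time since last dose, also to be tabulated: "Deaths within 30 days from last dose administration and deaths beyond this period up to 90 days follow-up and reasons for them". The 90-day limit matches the follow-up in Protocol 4.1.1.3: "The Safety Follow-up period will be 30 days and 90 days after the last dose of avelumab".

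SAP 15.2.2 (Deaths) defines three summaries, shown by cohort dose level:

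- a total over the whole study, split by primary reason;
- a window counted from the end of treatment, with no split by reason: "Number of deaths within 30 days after last dose of study intervention";
- a window counted from the start of treatment, again with no split by reason: "Number of deaths within 60 days after first dose of study intervention".

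The accompanying listing gives date and cause of death, first and last administration of each intervention, and relatedness. It flags deaths within 30 days of last intervention and within 60 days of first intervention, but not deaths in the later window.

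SAP Section 4 says the plan is based on Protocol Section 9. SAP Section 7 says the protocol's methods were adopted and then lists only pharmacokinetic parameters as changed.

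**The concern.** A safety table that the protocol commits to is missing from the SAP, and the section meant to record such changes does not mention it. Someone who relied on SAP Section 7 would expect the clinical study report to show deaths in the later part of the protocol's own follow-up, by reason and dose level. It would not. The only other time-limited row is counted from first dose, so it answers a different question (early mortality after starting treatment) from the one the protocol asks (mortality after stopping).

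The SAP does treat 90 days after last dose as relevant elsewhere: Appendix I accepts immune-related events with onset up to 90 days after last dose. Its death summary does not use that window.

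**Working it through.** The plan gives no figure to reproduce, so the check has three parts.

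**1. The two documents side by side**

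| Output | Protocol 9.4.2 | SAP 15.2.2 |
|---|---|---|
| All deaths after first dose, with reasons | Yes | Yes |
| Deaths up to 30 days after last dose | Yes | Yes |
| Reasons for that window | Yes | No |
| Deaths after 30 and up to 90 days from last dose, with reasons | Yes | No row, no flag |
| Deaths up to 60 days after first dose | No | Row and flag |

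**2. Can the 60-day row stand in for the missing window?**

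Put first dose on Day 1 and last dose on Day L. A death k days after last dose is (L − 1) + k days after first dose. It is in the missing window if k runs from 31 to 90, which is 60 days. It is in the SAP's 60-day row if (L − 1) + k ≤ 60, that is, k ≤ 61 − L. The number of shared days is therefore (61 − L) − 30 = 31 − L, and zero once L reaches 31.

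| Last dose on | Shared days, of 60 |
|---|---|
| Day 1 | 30 |
| Day 15 | 16 |
| Day 29 | 2 |
| Day 30 | 1 |
| Day 31 or later | 0 |

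The 60-day row covers half of the missing window for someone who stops after Day 1, and none of it for anyone still being dosed on Day 31.

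**3. Do the adverse event tables fill the gap?**

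SAP 9.1 ends the on-treatment period 30 days after last intervention, or earlier at death or the day before new anticancer drug therapy. SAP 15.1 defines a TEAE by onset or worsening in that period, not by date of death. So:

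- An event starting on day 20 after last dose and fatal on day 50 is in the tables of TEAEs leading to death, provided no new anticancer drug therapy started before its onset.
- An event starting on day 45 and fatal on day 60 is not. The fatal irAE table in SAP 15.2.4 does not catch it either, being limited to treatment-emergent events.

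The second kind of death appears only in the overall death count by reason and in listings, unless early discontinuation also brings it into the 60-day row.

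**Possible number of deaths.** The documents give no survival figure. As an assumption, let survival after last dose be exponential with median m months (30.4375 days each). The share dying after day 30 and by day 90 is exp(−ln2 × 30/(30.4375m)) − exp(−ln2 × 90/(30.4375m)).

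| Assumed median | Share in window | Of 18 participants | Of 66 participants |
|---|---|---|---|
| 4 months | 0.244 | 4.4 | 16.1 |
| 6 months | 0.182 | 3.3 | 12.0 |
| 9 months | 0.131 | 2.4 | 8.6 |

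18 and 66 are the minimum and maximum totals in the protocol synopsis. These are deaths from any cause, spread over three study parts and several dose levels.

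**The case against.** The strongest reply is that little information is lost. The deaths stay in the overall count, which SAP 15.2.2 gives by primary reason and by dose level. The listing holds the death date, cause and last-dose dates, and with 3 to 6 participants planned per dose level the window can be read off by hand. SAP 15.2.3 flags SAEs with onset outside the on-treatment period, SAP 15.2.4 lists late irAEs separately, and SAP 14.5 estimates overall survival by dose level. The study is exploratory and tests no hypothesis. All of this stands, and it limits the weight of the point. It does not remove the mismatch: a planned tabulation is absent and the absence is undeclared.

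A reader might go further in four ways that the documents do not support.

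- **That fatal events in this window escape both the death rows and the TEAE tables.** TEAEs are defined by onset or worsening, and the 60-day row catches some early discontinuers. The statement is true only for late-onset events after a later last dose.
- **That the RP2D rests on this table.** Protocol 6.6.4 lets 30-day and 90-day follow-up data guide the RP2D, but through committee review during the study. SAP Section 4 leaves those outputs to the SMC Charter. SAP 6.1 places the interim safety analyses after RP2D selection, and SAP 6.2 places the final analysis after study end.
- **That the missing window is where radiation toxicity would be seen.** Protocol 4.1.1.3 sets separate radiotherapy follow-up at 30 days, 3 months and 12 months after radiotherapy.
- **That the SAP deliberately exchanged one window for the other.** Nothing says so; an oversight is equally possible.

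**Conclusion.** The mismatch is real and undeclared. SAP 15.2.2 leaves out the second death window planned in Protocol 9.4.2, gives reasons only for deaths overall, and adds a row that shares no days with the missing window once last dose is on Day 31 or later. The consequence is a gap in descriptive safety reporting, chiefly for fatal events with onset more than 30 days after last dose. No primary endpoint or dose decision changes.

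The comparison and the day count need no outside figure, only the reading that the SAP's row counts a death falling up to 60 days after the first-dose date. The possible count, about 2 to 4 deaths at minimum enrolment and 9 to 16 at maximum, rests entirely on the assumed survival curve and does not measure missed toxicity. On the same curve the omitted window would hold more deaths than the one kept, largely because it is twice as long (60 days against 30), so that comparison should carry no weight.

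One ambiguity needs settling at the same time. The SAP counts from last dose of study intervention, while the 90-day follow-up in Protocol 4.1.1.3 counts from last avelumab. Protocol 6.9.1 and 7.1 allow M3814 to continue after avelumab stops, so the two dates can differ.

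**What to change.** In SAP 15.2.2:

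1. Add a row for deaths more than 30 and up to 90 days after last dose of study intervention, in total and by primary reason.
2. Give primary reason for the row covering the first 30 days as well.
3. Add a listing flag for the new window.
4. State whether last dose means the last of any intervention or the last avelumab infusion.

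Keep the 60-days-from-first-dose row as an addition and record it in SAP Section 7.

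The cost is a few table rows and one flag. All are derived from the death date, cause and last-administration dates that the listing already requires, so no new data collection is needed.

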#### 15.2.3 Serious Adverse Events

Analysis set: SAF

Please refer to Section 15.1.1 for details on SAE summaries.

The listings of all SAEs will also be provided with the relevant information with a flag for SAEs with onset outside of the on-treatment period.

# 15.2.4 Adverse Events of Special Interest

Analysis set: SAF

The frequency (number and percentage) of subjects with each of the following will be presented for treatment emergent irAEs, by dose level:

- irAEs leading to death, by SOC and PT
- irAEs, by SOC and PT
- irAEs leading to discontinuation, by SOC and PT
- irAEs, Grade ≥ 3, by SOC and PT
- irAEs by SOC and PT and worst grade
- Serious irAEs by SOC and PT

The listing of all irAEs will also be provided with the relevant information with a flag for irAEs with onset outside of the on-treatment period. A separate listing of irAEs with onset after the ontreatment period will also be provided.

The frequency (number and percentage) of subjects with each of the following will be presented for treatment emergent IRRs, by dose level:

- IRRs leading to death, by SOC and PT
- IRRs leading to discontinuation, by SOC and PT
- IRRs, by SOC and PT
- IRRs, Grade ≥ 3, by SOC and PT
- Serious IRRs, by SOC and PT

Timing of first onset of an IRR (infusion 1, infusion 2, infusion 3, infusion 4 or later) will be provided.

The listing of all IRRs will also be provided with the relevant information with a flag for IRRs with onset outside of the on-treatment period.

# 15.3 Clinical Laboratory Evaluation

Analysis set: SAF

# 15.3.1 Hematology and Clinical Chemistry Parameters

All statistical analyses of laboratory values will be performed using SI units.

Any subject with an abnormal hematology or chemistry result will have all records for the parameter with the abnormal result included in a listing. Pertinent details, including value, change from baseline, normal range indicator, and toxicity grade (where applicable) will be provided.

Quantitative data will be examined for trends in actual values and the change from baseline through presentation of boxplots shown over time, at each visit. In addition, a boxplot of the change from baseline to the worst on-treatment record for each parameter will be produced.

Listings will include all the hematology and chemistry laboratory parameters as available in the database with the all corresponding relevant information.

#### Parameters with CTCAE grade defined

Please see Appendix II – NCI-CTC Gradable and Non-Gradable Safety Laboratory Test Parameters and Direction(s) of Abnormality for a list of the CTCAE-gradable parameters.

Laboratory toxicities will be tabulated (count and percentage) for each gradable parameter by the worst on-treatment CTCAE grade. Shifts from baseline to worst CTCAE grade during the ontreatment period will also be tabulated. For some parameters (indicated in Appendix II), the ontreatment grading is dependent upon the baseline grading; in such cases, the baseline grading

(normal vs. abnormal) will be displayed together with the on-treatment grading in the tabular summaries

The denominator to calculate percentages for each laboratory parameter is the number of patients in the cohort dose level. Subjects without baseline or post-baseline results for a given parameter will be presented in the "Missing" category and will contribute to the denominator.

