9.4.3 Other Analyses

General Considerations

The following statistics will be used to summarize the study data (e.g. Baseline Characteristics) unless otherwise specified:

- Continuous variables: number of nonmissing observations, mean, standard deviation, median, minimum, and maximum, 95% confidence intervals for the mean, as appropriate.
- Categorical variables: frequencies and percentages.
- The calculation of proportions will be based on the number of participants in the analysis set of
 interest, unless otherwise specified in the study Integrated Analysis Plan.
- Participants will be summarized by dose level for Part A, Part B, and Part FE.

Baseline

In general, the last nonmissing measurement prior to the first study intervention will serve as the Baseline measurement.

Estimation of Individual PK Parameters:

- PK, immunogenicity, pharmacodynamic, and biomarker exploratory analyses will be specified in the Integrated Analysis Plan finalized before database lock. Integrated analyses across studies, such as the population PK analysis and pharmacodynamic analyses will be presented separately from the main clinical study report (CSR).
- Noncompartmental computation of PK parameters will be performed using the computer program Phoenix® WinNonlin® Version 6.3, or higher (Certara, L.P., [name]).
- The statistical software SAS® (Statistical Analysis System, SAS-Institute, Cary NC, USA, windows Version 9.1 or higher) may be used to produce tables, listings and figures and in the calculation of PK Parameters if appropriate.

PK concentrations of avelumab, M3814, and/or metabolites will be summarized descriptively and may be pooled with data from other studies to conduct population PK analysis.

Full PK, pharmacodynamic, and biomarker exploratory analyses will be specified in the Integrated Analysis Plan finalized before database lock. The population PK analysis, if conducted, and pharmacodynamic analyses will be presented separately from the main CSR.

ADA/Immunogenicity

Individual participants will be categorized across all valid ADA results as ever-positive versus never-positive. ADA ever-positive participants will be further categorized as pre-existing, including treatment-boosted, versus treatment-emergent. ADA treatment-emergent participants will be further subdivided into transient positive and persistent positive.

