## Presentation of continuous and qualitative variables

Continuous variables will be summarized using descriptive statistics i.e., number of subjects considered and number of missing values, [i.e., n (missing)], mean, median, standard deviation (StDev), minimum, maximum and first and third quartile (Q1 and Q3). As per general reporting conventions, mean, median, Q1, and Q3 will be displayed with one more decimal place than the raw data; StDev will be displayed using two more decimal places than the raw data. Percentages will be reported to one decimal place. Rounding will be performed to closest integer/decimal using the common mid-point between the two consecutive values – e.g., 5.1 to 5.4 will be rounded to an integer of 5, and 5.5 to 5.9 will be rounded to an integer of 6.

Qualitative variables will be summarized by frequency counts and percentages. Unless otherwise stated, the calculation of proportions/percentages for a given qualitative variable will include subjects with missing values in the denominator. When applicable, counts of missing observations for a qualitative variable will be presented on summary tables.

Unless otherwise specified, percentages will be based on the number of subjects in the analysis set used for the given summary.

For presentation of PK results please refer to Section 9.2.

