#### Parameters with no CTCAE grade defined

Laboratory abnormalities will be tabulated (count and percentage) for each non-gradable parameter by the worst on-treatment abnormality. Shifts from baseline to worst abnormality (separately for high and low criteria) during the on-treatment period will also be tabulated. The denominator to calculate percentages for each laboratory parameter is the number of patients in the cohort dose level. Subjects without baseline or post-baseline results for a given parameter will be presented in the "Missing" category and will contribute to the denominator.

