# 15.4 Vital Signs

Analysis set: SAF

The maximum changes of vital sign measurements from baseline to maximum change during the on-treatment period will be grouped as follows:

Table 9: Vital Signs Summary Categories

Vital Sign Baseline Category	Change from Baseline Category
Body temperature increase	<1°C, 1-<2°C, 2-<3°C, ≥3 °C
Heart rate increase from baseline <100 bpm; ≥ 100 bpm	≤20 bpm, >20 – 40 bpm, >40 bpm
Heart rate decrease from baseline <100 bpm; ≥ 100 bpm	≤20 bpm, >20 – 40 bpm, >40 bpm
SBP increase from baseline <140 mmHg; ≥ 140 mmHg	≤20 mmHg, >20 – 40 mmHg, >40 mmHg
SBP decrease from baseline <140 mmHg; ≥ 140 mmHg	≤20 mmHg, >20 – 40 mmHg, >40 mmHg
DBP increase from baseline <90 mmHg; ≥ 90 mmHg	≤20 mmHg, >20 – 40 mmHg, >40 mmHg
DBP decrease from baseline <90 mmHg; ≥ 90 mmHg	≤20 mmHg, >20 – 40 mmHg, >40 mmHg
Respiration rate increase from baseline <20 bpm; ≥ 20 bpm	≤5 bpm, >5 – 10 bpm, >10 bpm
Respiration rate decrease from baseline <20 bpm; ≥ 20 bpm	≤5 bpm, >5 – 10 bpm, >10 bpm

The following summaries will be prepared for vital sign parameters as grouped above considering only participants with post-baseline values:

- Maximal shifts (changes in categories)
- Listing of highest change per participant

An additional participant data listing will present all pertinent vital signs details collected throughout the course of the study.

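### The SAP divides laboratory toxicity counts by the whole cohort where the protocol admits only participants with post-baseline values; the change is undeclared and lowers the percentages whenever results are missing

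*SAP*

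**What the plan says.** Protocol 9.4.2, under Laboratory Variables, states that "The worst on-study grades after the first study intervention will be summarized", then adds shifts in grade and the presentation of variables without CTCAE grades, and closes with "Only participants with postbaseline laboratory values will be included in these analyses".

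SAP 15.3.1 covers the same tables. For gradable parameters it says "The denominator to calculate percentages for each laboratory parameter is the number of patients in the cohort dose level", and the subsection on non-gradable parameters repeats the rule. Both then deal with absent data: "Subjects without baseline or post-baseline results for a given parameter will be presented in the" *Missing* category, and these participants stay in the denominator.

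The neighbouring section, SAP 15.4, prepares the vital-sign summaries "considering only participants with post-baseline values", which is the protocol's laboratory rule applied to another domain. SAP Section 7 says the protocol's methods were adopted and lists one group of changes, PK parameters that will no longer be calculated. It does not mention laboratory denominators.

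**The concern.** Grade 3 or higher laboratory abnormality is a secondary safety endpoint in Parts A, B and FE. The two documents give different percentages for it as soon as one treated participant has no post-baseline result, and a reader who relies on SAP Section 7 would not know that the protocol's rule had been replaced. With 3 to 6 participants planned per dose level, one person moves the percentage visibly.

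A second problem lies in the wording about absent results. It covers participants without a baseline **or** a post-baseline result. Read literally, someone with an on-treatment Grade 3 value but no baseline for that parameter is tabulated as *Missing* in the worst-grade table, so an observed abnormality leaves the numerator.

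**Working it through.** Neither document states a laboratory rate or an expected amount of missing data, so there is no planned figure to reproduce. The check is direct arithmetic.

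**Inputs**
- N, participants at a dose level: 3 to 6 (Protocol 6.6.2 and 6.6.4). Part A in total: up to 30.
- x, participants with a worst on-treatment grade of 3 or higher: assumed 1 or 2.
- m, treated participants with no post-baseline result for the parameter: not given, assumed 0 to 3.
- The protocol's restriction is read per parameter, which is how the SAP applies its own rule.

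**Step 1: effect of the denominator.** Protocol percentage = x/(N − m). SAP percentage = x/N. The ratio of SAP to protocol is (N − m)/N, which never exceeds 1.

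| N | m (assumed) | x | Protocol rule | SAP rule |
|---|---|---|---|---|
| 3 | 1 | 1 | 1/2 = 50.0% | 1/3 = 33.3% |
| 6 | 1 | 1 | 1/5 = 20.0% | 1/6 = 16.7% |
| 6 | 1 | 2 | 2/5 = 40.0% | 2/6 = 33.3% |
| 6 | 2 | 2 | 2/4 = 50.0% | 2/6 = 33.3% |
| 30 | 3 | 2 | 2/27 = 7.4% | 2/30 = 6.7% |
| any | 0 | any | x/N | x/N |

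One missing participant lowers the percentage by a relative 1 − 5/6 = 17% in a cohort of six and 1 − 2/3 = 33% in a cohort of three. In a whole-part column the effect is small.

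**Step 2: effect of a missing baseline.** Take N = 6, everyone with a post-baseline result, and two true cases, one of them without a baseline. The protocol rule gives 2/6 = 33.3%. The SAP wording moves one case to *Missing* and gives 1/6 = 16.7%.

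**Step 3: does a general rule settle the conflict?** Protocol 9.4.3 bases proportions on the analysis set of "interest, unless otherwise specified in the study Integrated Analysis Plan". SAP 9.1 sets the default that "the calculation of proportions/percentages for a given qualitative variable will include subjects with missing values in the denominator". Both are general provisions. The closing sentence of Laboratory Variables is a specific rule about who enters these analyses, and a general default does not displace it without a declared change.

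**The case against.** The strongest reply is that the protocol lets the analysis plan choose denominators and defers further safety detail to it, so the SAP did what it was invited to do. That leaves the sponsor free to choose the whole-cohort rule. It does not explain why SAP Section 7 is silent, or why vital signs follow the opposite rule.

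It can also be argued that the protocol's closing sentence refers only to its own paragraph, on shifts and non-CTCAE variables, and not to worst grade in the paragraph before. The wider reading is more natural. Even on the narrow one, the SAP's shift tables and non-gradable parameters still conflict with it.

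Three stronger inferences are tempting, and the documents do not support them.

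- *That the Grade 3 or higher rates are understated.* The gap appears only if a treated participant lacks a result, and no such rate is given. Nor is either convention neutral: leaving out missing participants assumes that they resemble those observed.
- *That unobserved participants are counted as having no abnormality.* They appear in their own category, not as Grade 0. A reader who sees one case, one missing and N = 3 can recompute the percentage.
- *That early drop-outs in Part A will largely be missing because the first scheduled on-treatment draw after Day 1 is Day 22.* Protocol Table 1 also schedules hematology and chemistry at the End of Treatment visit, required within 7 days of the decision to discontinue, and at the 30-day follow-up. SAP 9.1 runs the on-treatment period to 30 days after last dose unless new anti-cancer drug therapy or death comes first, and counts unscheduled results towards worst grade. Part B adds draws on Days 5 and 12.

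On the missing-baseline problem, eligibility testing makes an absent baseline unlikely for neutrophils, platelets, hemoglobin, bilirubin, AST, ALT and renal function. It is less remote for gradable parameters not named in those criteria, such as CPK, LDH, GGT and urate. The value is not lost altogether, because SAP 15.3.1 lists all records of a parameter with an abnormal result, with grade where applicable. The table itself would still be wrong, and a reader could not correct it from the table alone.

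**Conclusion.** The conflict between Protocol 9.4.2 and SAP 15.3.1 is explicit and undeclared, and should be resolved before the tables are programmed. Its numerical effect is conditional: the SAP percentage is (N − m)/N times the protocol percentage, hence equal when m = 0 and lower when both m and x exceed 0. In cohorts of 3 to 6 with one participant missing, the relative reduction is 17% to 33%. These sizes rest on assumed values of m. The missing-baseline wording is a separate defect, less likely to arise but able to remove an observed case from the tabulated count.

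The consequence is confined to descriptive secondary safety tables. A reader might infer that dose selection is affected. The documents do not support that for the model: under Protocol 9.4.2 it uses only the Dose Escalation Analysis Set, which the SAP calls the DLT Analysis Set, and outputs for the Safety Monitoring Committee are specified in its charter.

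**What to change.** In SAP 15.3.1, for both gradable and non-gradable parameters:

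1. For worst on-treatment grade or abnormality, use participants with at least one post-baseline value for that parameter as the denominator, and print n evaluable and n missing beside it.
2. Count a post-baseline Grade 3 or higher value even when baseline is missing. For the seven Appendix II parameters whose grading depends on baseline (ALT, AST, alkaline phosphatase, GGT, total bilirubin, creatinine, eosinophils), state how such a value is graded, for example against ULN as if baseline were normal, with a flag.
3. Base shift-table percentages on participants with a post-baseline value and include a baseline-missing row, so that these tables also follow Protocol 9.4.2.

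If the sponsor prefers the whole-cohort denominator, declare it in SAP Section 7 and report n evaluable with each percentage. Item 2 is still needed in that case.

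The cost is SAP wording and a changed denominator in the table programs. No new data are required.
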